# **3. PRIMARY AND SECONDARY VARIABLES**

## **3.1** General principles taken for analysis variables

#### 3.1.1 Study Day Definition

For the purposes of the data summaries, Study Day 1 is defined as the first date of study treatment. For visits (or events) that occur on or after first date of study treatment, study day is defined as:

(date of visit [event] - first date of study treatment + 1).

For visits (or events) that occur prior to first date of study treatment, study day is defined as:

(date of visit [event] - first date of study treatment).

There is no Study Day 0.

For listings (such as for AEs/SAEs that include the derivation of "days since last dose", this is defined as:

(event date - date of last dose).

Events that occur on the same day as the last dose of study treatment will therefore be described as occurring zero days from the last dose of study treatment.

## **3.1.2 Duration of Type 2 Diabetes**

Duration of T2DM is calculated as the number of years from T2DM diagnosis date to informed consent date:

(consent date - diagnosis date +1) / 365.25.

The duration of diabetes will be included in the baseline diabetes characteristics listing.

Statistical Analysis Plan Amendment Study Code D1683C00005 Edition Number 4.0 Date 09th Aug 2017 If the date T2DM was diagnosed is partially missing, the following rules will take effect:

- Missing day, but month and year are present: the day will be imputed as the 15th day of the month.
- Missing day and month, but year is present: the day and month will be imputed as 30 June of the year (provided that the imputed date is less than the consent date).
- Missing year, but day and month are present: No imputations will occur, and the patient will be excluded from all summaries related to duration of T2DM.
- Missing day, month and year: No imputations will occur, and the patient will be excluded from all summaries related to duration of T2DM.
- If any such imputed date falls after the consent date, then the diagnosis date will be taken as equal to the consent date.

These durations, even if partially imputed, will be listed. However, only the portion of the date of diagnosis actually observed, rather than imputed dates, will be displayed in listings.

#### 3.1.3 Definition of Baseline Measurements

Unless otherwise stated, for each patient, baseline value of a parameter (e.g., efficacy laboratory parameter, safety laboratory test) is defined as the last assessment on or prior to the date of the first dose of the study medication.

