## 4.1 Screening Visit

Procedures will be performed according to the Study Plan Table 1.

Failure to meet the HbA1c inclusion criterion is the main reason for screening failure in diabetes treatment studies. Therefore, in this study, sites need to mandatorily perform a prestudy screening assessment (at Week -3) within 1 week prior to enrolment visit, which will comprise of a collection of 1 non-fasting blood sample to determine HbA1c at the central laboratory. Investigators will screen only patients who are potentially eligible for the study based on their medical conditions and existing therapies, and only those who are expected to meet all entry criteria at Enrolment (Visit 1).

In order to be considered for screening, patients must:

- 1. Be  $\geq$ 18 years old at time of informed consent.
- 2. Have a documented diagnosis of T2DM.
- 3. Currently treated with a stable MTD (≥1500mg/day) of metformin therapy and not have received any other antihyperglycaemic therapy within 8 weeks from the expected date of Enrolment (Visit 1).

At this Screening visit, the following will be performed:

- 1. Abbreviated informed consent to the pre- study screening procedures will be obtained (see Section 10.4.1).
- 2. A blood sample will be collected for measurement of HbA1c by a central laboratory. Fasting is not required.
- 3. Verification of current metformin therapy

Patients with HbA1c result of  $\geq$ 7.5% to  $\leq$ 10.0% assessed based on central laboratory results from screening visit will be scheduled for an enrolment visit in approximately 7 days. Patients should be fasting at the next visit (Enrolment, Visit 1) and a full ICF will be obtained before any assessments at that visit are initiated.

Note: Re-testing of HbA1c is permitted once within one month of the initial screening visit if central laboratory result of HbA1c is >7.0% and <7.5% or >10% and <10.5%.

All patients who are screened should be listed on a patient screening log. A screening code will be created for all screened patients by the site personnel. Patients with re-tested HbA1c at screening will have the same screening code. This code will identify screening laboratory results including retest results together with date of birth and gender.

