## 4.2.1 Enrolment visit (Visit 1, Week -2)

Patients on a stable, MTD of metformin monotherapy  $\geq 1500$ mg/day for the last 8 weeks prior to enrolment with an HbA1c  $\geq 7.5\%$  to  $\leq 10.0\%$  will be eligible to enter the study. The patient should maintain the prescribed stable dose of metformin for the duration of the study.

Visit 1 (Enrolment) should take place approximately 1 week after Screening visit. At Visit 1, informed consent for Protocol D1683C00005 will be obtained prior to performing any protocol-required procedures. Patients will be assessed to ensure that they meet eligibility criteria. Patients who do not meet these criteria must not be enrolled in the study and will be considered screen failures.

Enrolment (Visit 1) procedures should be scheduled for at least 1 day later than the day of informed consent signature if the patient is not in a fasting state on the consent date.

The following will be performed during this visit:

- 1. Informed consent will be obtained.
- 2. E-code will be assigned from IVRS/IWRS.
- 3. The patient's demography and complete medical history will be recorded.
- 4. Inclusion and exclusion criteria will be verified.
- 5. A complete physical examination will be conducted (see Section 5.2.2).
- 6. Vital signs (sitting systolic and diastolic BP and Heart Rate) will be measured (see Section 5.2.3).
- 7. Body weight and height will be measured (see Section 5.1.3 and 5.1.4).
- 8. BMI will be calculated.
- 9. All prior medications (prescription medications within 3 months) and concomitant medications (including over the counter and herbal/nutritional supplements) will be reviewed.

- 10. Blood samples will be collected for the following laboratory assessments:
  - Clinical chemistry and Hematology (see Section 5.2.1)
  - eGFR (MDRD) (see Section 5.2.1)
  - FPG (samples for central laboratory testing, see Section 5.2.1)
  - Hepatitis screening (hepatitis B surface antigen, antibody to hepatitis B core antigen IgM, and hepatitis C virus antibody)
  - Thyroid Function (TSH)
- 11. Urine will be collected for following (see Section 5.2.1)
  - Urinalysis
  - Urinary pregnancy test for beta human chorionic gonadotropin (βhCG) for female patients (WOCBP only)
  - Hematuria Dipstick and/or Microscopic Urinalysis
- 12. AEs/SAEs will be reviewed.
- 13. Diet and Exercise counseling will be provided.
- 14. Glucose meter and supplies and instructions will be provided.
- 15. Patient diary and instructions will be provided.

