## 8.2 Sample size estimate

The mean change from baseline in HbA1c at Week 24 will be assessed comparing the saxagliptin plus dapagliflozin treatment group versus the saxagliptin treatment group and versus the dapagliflozin treatment group.

Power calculations for longitudinal repeated measures analyses depend on many factors, including the pattern of drop out over time and correlations among the various time points included in the model. The choice of these parameters will affect any estimates of power and their true values may not be known. Based on comparisons of results of longitudinal repeated measures analyses and analysis of covariance using last observation carried forward (ANCOVA with LOCF) from previous diabetes trials, the estimated standard errors of the treatment differences were similar between analyses. Therefore, power calculations are based on ANCOVA with LOCF, with the expectation that this will provide a good estimate of the power for the primary analysis using a longitudinal repeated measures model.

A sample size of 300 patients per group will provide at least 90% power to simultaneously detect a difference in mean change from baseline to week 24 in HbA1c of -0.30 (%) for both primary endpoint comparisons of saxagliptin / dapagliflozin vs its components at the 2-sided

alpha = 0.05 level. This assumes a common standard deviation of 1.0% and a 3% non-evaluability rate.

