# 8.5 Methods for statistical analyses

Efficacy analyses will be run for the FA population and for the PP population if more than 10% of patients from the FA population are excluded from the PP population for important protocol deviations.

All analyses related glycaemic variables (for example, HbA1c) will be done using values regardless of rescue/intensification of treatment or discontinuation of the study treatment. Sensitivity analyses will be conducted for the primary endpoint excluding the data after rescue or more than 8 days after discontinuation of the study treatment.

The primary endpoint will be tested for saxagliptin plus dapagliflozin versus saxagliptin and dapagliflozin arms simultaneously at the alpha = 0.05 level (two sided). The secondary endpoints then will be tested sequentially as follows:

1. saxagliptin plus dapagliflozin versus saxagliptin on percent of patients achieving a therapeutic glycaemic response, defined as a HbA1< 7.0% at Week 24

- 2. saxagliptin plus dapagliflozin versus dapagliflozin on percent of patients achieving a therapeutic glycaemic response, defined as a HbA1< 7.0% at Week 24
- 3. saxagliptin plus dapagliflozin versus saxagliptin on mean change from baseline in fasting plasma glucose at Week 24
- 4. saxagliptin plus dapagliflozin versus dapagliflozin on mean change from baseline in fasting plasma glucose at Week 24
- 5. saxagliptin plus dapagliflozin versus saxagliptin on mean change from baseline in total body weight at Week 24

Each comparison will be tested at the alpha = 0.05 (two-sided) level.

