## 4.2.4.1 Primary efficacy outcome variable

A longitudinal repeated measures analysis using 'direct likelihood' will be performed. The SAS procedure PROC MIXED will be used. The preferred model will include the fixed categorical effects of treatment, week and treatment-by-week interaction as well as the continuous fixed covariates of baseline measurement and baseline measurement-by-week interaction.

The following model will be used:

 $C_{ijk} = intercept + \beta_1 \left[ M_{baseline,ij} \right] + \tau_i + \alpha_k + (\alpha \tau)_{ik} + (\alpha M_{baseline})_{ijk} + error_{ijk}$ 

where

- Cijk is the change from baseline for patient j in treatment group i at time k,
- $\beta_1$  is the slope coefficient for the baseline measurement,
- Mbaseline,ij is the baseline measurement of patient j in treatment group i,
- $\tau_i$  is the mean effect of treatment group i,
- $\alpha_k$  is the mean effect at time k
- $(\alpha \tau)_{ik}$  is the interaction term between treatment group i and time k.
- $(\alpha M_{baseline})_{ijk}$  is baseline measurement-by-week interaction term for patient j in treatment group i at time k, and
- error  $_{ijk}$  is the error term for patient j in treatment group i at time k.

An unstructured matrix for the within-patient error variance-covariance will be used. The denominator degrees of freedom will be calculated according to the Kenward-Roger method.

Statistical Analysis Plan Amendment Study Code D1683C00005 Edition Number 4.0 Date 09th Aug 2017 In case of non-convergence of the preferred model or memory space issues, the following back-up models are defined:

- The first backup model is the same as the preferred model but the Kenward-Roger method will be replaced by Satterthwaite approximation.
- The second backup model is the same as the preferred model but without the term for baseline measurement-by-week interaction.

The second back-up model will only be provided if the first back-up model does not converge or has memory issues.

The model will provide least-squares mean estimates, SE and 2-sided 95% confidence intervals for mean change at all time points within and between treatments.

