#### 4.2.4.2 Secondary efficacy variable

The primary endpoint will be tested for saxagliptin plus dapagliflozin versus saxagliptin and dapagliflozin arms simultaneously at the alpha = 0.05 level (two sided). In order to protect the overall type I error rate, the interpretation of the statistical significance of treatment comparisons for each secondary efficacy endpoint will be done using a stepwise procedure. The secondary endpoints then will be tested sequentially as follows:

- 1- saxagliptin plus dapagliflozin versus saxagliptin on percent of patients achieving a therapeutic glycaemic response, defined as a HbA1< 7.0% at Week 24
- 2- saxagliptin plus dapagliflozin versus dapagliflozin on percent of patients achieving a therapeutic glycaemic response, defined as a HbA1< 7.0% at Week 24
- 3- saxagliptin plus dapagliflozin versus saxagliptin on mean change from baseline in FPG at Week 24
- 4- saxagliptin plus dapagliflozin versus dapagliflozin on mean change from baseline in FPG at Week 24
- 5- saxagliptin plus dapagliflozin versus saxagliptin on mean change from baseline in total body weight at Week 24

Each comparison will be tested at the alpha = 0.05 (two-sided) level.

The analysis of the change from baseline for FPG and total body weight at week 24 will be performed using the same longitudinal repeated measures model as for the primary efficacy endpoint.

The proportion of subjects achieving a therapeutic glycemic response (defined as HbA1c <7.0%) at Week 24 will be summarized by treatment group and compared between treatment groups using the methodology of Zhang, Tsiatis, and Davidian [3], and Tsiatis, Davidian, Zhang, and Lu [4]. 95% confidence intervals for the response rate within each treatment group as well as for the difference in response rates between treatment groups will be calculated with adjustment for baseline HbA1c. As defined in Section 3.1.6 patients who did not have A1c measurement at week 24 will be treated as those who did not achieve a therapeutic glycaemic response.

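### The repeated measures models adjust for one pre-dose value only, leaving Visit 1 FPG and, less importantly, screening HbA1c unused as covariates: forgone precision, not an error

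*SAP*

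**What the plan says.** SAP 3.1.3: the baseline value of a parameter "is defined as the last assessment on or prior to the date of the first dose of the study medication". That is normally the Visit 2 (Week 0) sample.

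SAP 4.2.4.1: besides treatment, week and their interaction, the primary HbA1c model has the "continuous fixed covariates of baseline measurement and baseline measurement-by-week interaction". Protocol 8.5.1 lists the same terms.

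SAP 4.2.4.2: the FPG and body weight analyses are "performed using the same longitudinal repeated measures model as for the primary efficacy" endpoint. The FPG model therefore carries one FPG value and no HbA1c value.

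Earlier values exist. At screening (Protocol 4.1), "A blood sample will be collected for measurement of HbA1c by a central laboratory". At enrolment (Protocol 4.2.1), the blood samples include "FPG (samples for central laboratory testing, see Section 5.2.1"). The Study Plan (Protocol Table 1) shows HbA1c at Visits 0 and 2 and FPG at Visits 1 and 2, and Protocol 4.3.1 has the Visit 2 samples drawn before dosing. The design summaries describe screening as allowed, but Protocol 4.1 makes it mandatory and Protocol 3.1 makes both earlier values inclusion criteria. SAP Table 1, item 1, already uses screening HbA1c to define the per protocol set.

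**The concern.** A single reading measures a patient's starting level with error. A second pre-randomisation reading usually sharpens the adjustment, and here it has already been collected. The earlier values serve for eligibility, and as a fallback if the Visit 2 value is missing, but they enter no efficacy model as covariates.

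The point matters most for FPG. The power statement covers HbA1c only, and the documents give no effect size, SD or power for FPG. FPG supplies steps 3 and 4 of the fixed testing sequence, and a miss at either step also closes step 5, body weight. Precision that needs no new sample is worth having where no margin is shown.

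**Working it through.** **1. The plan's own figure.** Protocol 8.2: "A sample size of 300 patients per group will provide at least 90% power to simultaneously detect a difference in mean change". The inputs there are 0.30 points of HbA1c in each comparison, SD 1.0 and 3% non-evaluable.
- Evaluable per arm: 300 × 0.97 = 291.
- One comparison: 0.30 / (1.0 × √(2/291)) − 1.96 = 3.62 − 1.96 = 1.66, so power is 95.1%.
- Both comparisons: at least 2 × 0.951 − 1 = 90.3%; 90.5% if independent; 91.5% with correlation 0.5 from the shared combination arm.

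The stated figure of at least 90% reproduces.

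**2. Formula for a second pre-dose covariate.** Let c be the correlation between the two pre-dose values, and r the correlation of each with the Week 24 value. Modelling change or the Week 24 value gives the same residual once baseline is a covariate.
- Residual variance with one value: 1 − r².
- With two: 1 − 2r²/(1 + c).
- Relative cut: r²(1 − c) / [(1 + c)(1 − r²)].

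This is a large-sample Week 24 approximation to the repeated measures model. The documents give neither c nor r; Protocol 8.2 itself says such parameters may be unknown. All values below are assumptions.

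**3. FPG, adding Visit 1 FPG (c 0.6-0.8, r 0.3-0.6).**

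| c | r | Cut in residual variance | Interval narrower by |
|---|---|---|---|
| 0.8 | 0.3 | 0.018/1.638 = 1.1% | 0.6% |
| 0.8 | 0.4 | 0.032/1.512 = 2.1% | 1.1% |
| 0.7 | 0.4 | 0.048/1.428 = 3.4% | 1.7% |
| 0.7 | 0.5 | 0.075/1.275 = 5.9% | 3.0% |
| 0.6 | 0.6 | 0.144/1.024 = 14.1% | 7.3% |

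These figures make no allowance for the 270 mg/dL entry cap on Visit 1 FPG, or for rescue.

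**4. HbA1c, adding screening HbA1c (c 0.80-0.95, r 0.4-0.6).** The formula gives 0.5% to about 6.2%. Screening HbA1c is limited to 7.5-10.0% by eligibility. Simulating that restriction (assumed source mean 8.0, SD 1.2) lowers the range to about 0.4-3.5%, for example from 1.8% to 1.2% at c = 0.9, r = 0.5. The interval narrows by 0.2-1.8%. If SD 1.0 is taken as the one-baseline residual SD, joint power moves from 91.5% to about 91.6-92.5%, worth about 1-11 of 300 patients per arm.

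**5. If the earlier value predicts less well.** With correlations r₁ (later value) and r₂ (earlier value), the cut is (r₂ − c·r₁)² / [(1 − c²)(1 − r₁²)]. With r₂ = 0.9·r₁ it is exactly 0 at c = 0.9. At c = 0.7 and r₁ = 0.5 it is (0.45 − 0.35)² / (0.51 × 0.75) = 2.6%, against 5.9% when both predict equally.

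**6. Adding baseline HbA1c to the FPG model.** A simulation of a latent glucose level per patient assumed within-patient FPG CV 8-12% and a Visit 1 to Visit 2 correlation of 0.5-0.7, with the entry limits applied. The FPG residual variance fell by 2.7-5.9% with Visit 1 FPG alone and by 3.7-10.1% with baseline HbA1c as well. It modelled no rescue or dropout, so it is supportive only.

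**The case against.** The planned models are valid, and choosing more covariates is a preference among valid analyses. That stands. A reader might infer that the last-value rule biases the comparison or disturbs type I error. It does neither, and the rule itself need not change.

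For HbA1c the gain is close to negligible. The earlier values are truncated by eligibility and precede any effect of the diet and exercise counselling that starts at Visit 1, so they may predict less well than the Visit 2 value. This stands, and it makes the HbA1c term optional.

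A reader might also infer that the loss must be larger for FPG. That is plausible, since Protocol 1.2 calls FPG a short-term measure, but the order can reverse: HbA1c at c = 0.85, r = 0.6 gives 4.6% (2.8% after range restriction), against 2.1% for FPG at c = 0.8, r = 0.4.

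It is tempting to credit the second FPG reading with the whole 3.7-10.1%, or 33-91 of 900 patients. Part of that comes from baseline HbA1c, a separate covariate. Visit 1 FPG alone gives 2.7-5.9% in that simulation, or 24-53 patients.

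It is equally tempting to call the FPG tests underpowered, or body weight likely to be lost. No FPG power can be computed from the documents, and the responder tests at steps 1 and 2 come first.

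Rescue weakens the case further. Rescue is triggered by high FPG (Protocol 4.4), and later values are still analysed (Protocol 8.5). That should loosen the link between pre-dose and Week 24 FPG and shrink the gain by an unknown amount.

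Finally, timing. The SAP is dated August 2017 and Protocol 9.3 expects completion in the third quarter of 2017. Late changes to the primary model need a stronger return than HbA1c offers. None of this removes the FPG case, which rests on data already in hand and a test with no stated margin.

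**Conclusion.** The point holds as a low-cost improvement in efficiency. Each model adjusts for one pre-dose value while a second pre-randomisation value is available for essentially every randomised patient. Adding it cannot raise the large-sample residual variance and leaves the treatment comparison unbiased.

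For FPG the size is roughly 1-14% of the Week 24 residual variance, with 5.9% as a mid-range example, and possibly less once rescue is allowed for. It rests on assumed correlations and on both readings predicting Week 24 equally well. For HbA1c it is about 0.4-3.5%, possibly nil, in a trial whose stated power already reproduces. The FPG covariates are the recommendation.

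**What to change.** Leave the change-from-baseline definition as it is.

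- **SAP 4.2.4.2, FPG model:** add Visit 1 FPG and baseline HbA1c, each with its interaction with week.
- **SAP 4.2.4.1, HbA1c model (optional):** add screening HbA1c with its interaction with week. Word it so that models defined as the same as the primary do not inherit the term unintentionally.
- **Retests:** state which FPG value is used after a Visit 1 retest, for example the mean used for eligibility in Protocol 3.1. After an HbA1c retest, use the qualifying value. State how results filed under the screening code link to the enrolment code.
- **Missing earlier value:** substitute the Visit 2 value, so that no patient is lost.
- **Back-up models:** say that the second back-up model drops the added covariate-by-week terms along with the baseline-by-week term.
- **Record:** list the change in SAP section 6 as a departure from Protocol 8.5.2 (and 8.5.1 if the HbA1c term is taken up), and fix it before unblinding, as Protocol 8.1 requires of amendments.

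Cost: slightly longer models and a documented SAP change. No new visits, samples or patients.

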#### 3.1.4 Change from Baseline

Change from baseline to any Week t is defined as follows:

$$C_{Week t} = M_{Week t}$$
 -  $M_{baseline}$ ,

where:

- CWeek t is the change from baseline at Week t,
- MWeek t is the measurement at Week t,
- Mbaseline is the measurement at baseline.#

The "Week t" to which a measurement belongs is determined using the conventions described in Table 2 below.

## 3.1.5 Visit Windows

For summaries of vital signs and laboratory data, assessments will be assigned to calculated visit windows (using study day) as described in Table 2 below.

Inclusion within the visit window should be based on the actual date and not the intended date of the visit. The window for the visits following baseline (including unscheduled visits) will be constructed in such a way that the upper limit of the interval falls half way between the two visits.

For laboratory and non-laboratory parameters, unless otherwise specified, if a patient has more than one measurement included within a window, the assessment closest to the target

day will be used. In case of ties between observations located on different sides of the target day, the earlier assessment will be used. In case of ties located on the same side of the target day (i.e. more than one value for the same day but different time), the value with the earlier entry date/time will be used.

| Assessment                   | Visit | Week | Target Day | Day Range |
|------------------------------|-------|------|------------|-----------|
| Screening/Baseline           | 0     |      |            |           |
| Post Baseline                | 1.5   |      |            | 2-22*     |
|                              |       |      |            | (1-22)    |
| Week 6                       | 2     | 6    | 43         | 23-64     |
| Week 12                      | 3     | 12   | 85         | 65-126    |
| Week 24/ End of
Treatment | 4     | 24   | 169        | 127-190   |
| Post Treatment               | 999   | РТ   |            | >190      |

Table 2 - Visit Windows

\* for vital signs and laboratory assessments only. These will only be displayed in the listings.

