## 4.4 Rescue therapy

During the double-blind treatment period of the trial, patients may be eligible for treatment with open-label rescue medication (see Table 6) to replace their blinded treatment regimen in order to treat ongoing hyperglycaemia. The sub-sections and table listed below define the lack of glycaemic control criteria for initiation of rescue medication.

Pre-specified glycaemic criteria (see Table 2), based upon repeat confirmatory central laboratory FPG have been established during the double-blind treatment period, starting at

Table 2 Criteria for Initiation of Rescue Therapy During the Randomised Treatment Period

Visit Period	Central Laboratory glycaemic parameters		
At Week 6	FPG >270mg/dL (15.0mmol/L)		
From Week 6 to Week 12 (Excluding Week 12)	FPG > 240 mg/dL (13.3 mmol/L)		
Week 12 to Week 24	FPG > 200mg/dL (11.1mmol/L)		

Week 6, to determine eligibility for open-label rescue medication.

Abbreviations: FPG Fasting plasma glucose

Patients with a central laboratory FPG value meeting the lack of glycaemic control criterion at a pre-specified visit will be scheduled for a follow-up visit (within 3 to 5 days) to obtain a second central laboratory FPG value and review the patients glucose meter readings. If the repeat central laboratory FPG value still meets the criterion, the patient must be rescued.

Patients who meet rescue criteria in the double-blind treatment period must first complete the Rescue Visit procedures before receiving open-label rescue medication to ensure that important trial endpoint measurements are collected.

Following completion of the Rescue Visit, rescued patients will be given open-label antidiabetic rescue medication (Saxagliptin 5mg and Dapagliflozin 10 mg as a first line or Insulin as a second line at Investigators discretion) and will discontinue study medication. Rescued patients will then continue in the double-blind treatment period according to their original visit schedule.

Note: Rescue medication (Saxagliptin 5mg and Dapagliflozin 10mg) will be provided by Sponsor in this study. Insulin will not be provided by Sponsor since it is part of patients standard of care.

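### SAP 3.1.5 lets a rescue-confirmation FPG replace the high scheduled value that triggered it when the scheduled visit was early: a small, avoidable selection on the outcome, clear only at Weeks 6 and 12

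*SAP*

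**What the plan says.** SAP 3.1.5 assigns laboratory values to windows by actual date and covers extra samples: "The window for the visits following baseline (including unscheduled visits) will be constructed in such a way" that each upper limit falls midway between two visits. Within a window, "if a patient has more than one measurement included within a window, the assessment closest to the target" day is taken. For ties, "In case of ties between observations located on different sides of the target day, the earlier assessment will be used". The scheduled sample has no priority.

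The section opens by speaking of summaries of vital signs and laboratory data. SAP 3.1.4 carries the rule into change from baseline, because the week "to which a measurement belongs is determined using the conventions described in Table 2 below". It therefore reaches efficacy FPG.

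Protocol 4.4 creates the extra sample. A patient whose FPG meets the rescue criterion "will be scheduled for a follow-up visit (within 3 to 5 days) to obtain a second central laboratory FPG value". The limits in Protocol Table 2 are above 270 mg/dL at Week 6, above 240 mg/dL between Weeks 6 and 12, and above 200 mg/dL from Week 12 to Week 24. Confirmed patients then have a Rescue Visit, whose procedures (Protocol 4.5) include another FPG.

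FPG change at Week 24 is a secondary endpoint, third and fourth in the test sequence (SAP 4.2.4.2). FPG at Weeks 6 and 12 is exploratory (SAP 4.2.4.3).

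**The concern.** The confirmatory sample exists only because the first value was high. A rule that can put it in place of the first value therefore selects the analysed value on the outcome. Part of any high reading is within-patient variation, so the repeat is lower on average even if nothing has changed. Patients below the limit have no repeat and keep their value.

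The effect is a downward shift in each arm's mean FPG, in proportion to the share of patients replaced. If that share is larger in the single-agent arms, their means fall further and the advantage of the combination is understated.

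**Working it through.** **Plan's own figure.** The documents give no FPG mean, SD, power or rescue rate. The only planning figure is for HbA1c: 300 × 0.97 = 291 evaluable per arm, difference 0.30, SD 1.0, two-sided 0.05. This gives 95.1% power per comparison and joint power of 90.5% (independent) or 91.5% (correlation 0.5), so the stated 90% reproduces. This point does not affect it.

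**Is the repeat in the same window?** Protocol Table 1 allows ±7 days. With a gap of 3 to 5 days the repeats fall as follows:

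| Visit | Target day | Repeat days | SAP window |
|---|---|---|---|
| Week 6 | 43 | 39–55 | 23–64 |
| Week 12 | 85 | 81–97 | 65–126 |
| Week 24 (if drawn) | 169 | 165–181 | 127–190 |

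**When does it replace the first value?** With the scheduled visit at offset d from target and the repeat g days later, the repeat is used when |d + g| < |d|.
- g = 3: d from −7 to −2, 6 of 15 whole-day offsets.
- g = 4: d from −7 to −3, 5 of 15 (d = −2 is a tie, so the earlier value stays).
- g = 5: d from −7 to −3, 5 of 15.

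With visits spread evenly over ±7 days the share is (6 + 5 + 5)/45 = 36%. With visit timing normal, SD 3 days, the shares are 31%, 20% and 20%, about 24% overall. On-time and late visits are never affected.

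**Size (all FPG inputs assumed).** Take arm mean μ, total SD s, within-patient SD w, limit L and replaced share f, with a = (L − μ)/s and φ the standard normal density:
- share above the limit: q = 1 − Φ(a)
- mean drop per replaced patient: (w²/s) × φ(a)/q
- shift in the arm mean: f × (w²/s) × φ(a)

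Central case: L = 200, s = 40, w = 15 (w²/s = 5.625), f = 0.356, means 150 (combination) and 165 (control).
- Combination: a = 1.25, φ = 0.183, q = 10.6%; shift 0.356 × 5.625 × 0.183 = 0.37 mg/dL; drop per replaced patient 9.7.
- Control: a = 0.875, φ = 0.272, q = 19.1%; shift 0.356 × 5.625 × 0.272 = 0.55 mg/dL (0.54 before simulation); drop per replaced patient about 8.1.
- Differential: 0.55 − 0.37 = 0.18 mg/dL towards zero.

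A simulation of 2,000,000 patients per arm agrees with these figures.

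Range at the 200 limit with f = 0.356:
- low end (means 150 and 165, s = 45, w = 10): 0.06 mg/dL
- high end (means 140 and 170, s = 35, w = 25): 1.17 mg/dL

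With f = 24% these scale by about two thirds. At the Week 6 limit of 270 (means 155 and 170, s 35 to 45, w 10 to 25) the differential is 0.01 to 0.09 mg/dL.

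**Scale.** The standard error of a difference with SD 40 is 40 × √(2/291) = 3.3 mg/dL. The central case is 0.18/3.3 = 5% of that, and the high end is 1.17/3.3 = 35%.

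**Carry-over to Week 24.** The model has treatment-by-week and baseline-by-week terms and unstructured covariance (SAP 4.2.4.1), so earlier visits influence the Week 24 estimate almost only through patients missing Week 24. At the 3% non-evaluable rate stated for HbA1c, an order-of-magnitude figure is 0.03 × 1.2 ≈ 0.04 mg/dL at most. More missing FPG at Week 24 would raise this.

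**The case against.** The rule is prespecified, blind to treatment and the same in every arm. If the arms do not differ, crossing rates and shifts are equal, so type I error is unaffected; where they do differ as expected, the bias is conservative. All of this stands.

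The 36% share is towards the high end. Protocol 4.4 does not say whether the 3 to 5 days run from the draw or from the result. If the gap were 8 days, the even-spread share would be 3/15 = 20%.

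A reader might infer two stronger points that the documents do not support.

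- **The Week 24 secondary endpoint is biased.** Protocol Table 2's last row runs to Week 24 without excluding it, whereas the row above explicitly excludes Week 12. But Protocol Table 1 dispenses rescue drug only at Visits 3 and 4, study drug is returned at Visit 5, and Protocol 4.4 describes rescue as replacing blinded treatment with patients then continuing their schedule. A repeat after a high Week 24 value may never be drawn.
- **The control arms are lowered more.** This needs more control patients above the limit. That is plausible for a combination expected to lower FPG further, but no crossing rates are given. In the central case the drop per replaced patient is slightly larger in the combination arm; the control shift is larger only because more patients are replaced.

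**Conclusion.** The gap in SAP 3.1.5 is real and minor. As written, the rule can replace a scheduled FPG with a later one only in patients selected for a high scheduled value, and no other text prevents it. The mechanism and the day arithmetic come from the documents. The size does not: it rests on assumed FPG means, SDs and visit timing, and its direction between arms is conditional on more control patients crossing the limit. On those assumptions the loss is usually a small fraction of one standard error at Week 12 and negligible at Week 6. HbA1c is not involved, and nothing here threatens the trial's validity. Week 24 FPG remains an open question rather than a demonstrated bias.

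**What to change.** Add to SAP 3.1.5: an FPG sample drawn to confirm a rescue criterion, or at the Rescue Visit that follows, does not replace the FPG from the Week 6, 12 or 24 visit that triggered it; it is used only when the window holds no such visit sample.

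This wording is safer than simply preferring the scheduled visit. Protocol 4.5 labels Rescue and early-termination assessments as Visit 5, Week 24, although they can fall in an earlier window, so the scheduled visit would be undefined for those patients.

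Protocol Table 1 and Protocol 4.4 (Table 2) should also be reconciled on whether a confirmatory FPG is taken after a high Week 24 value.

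The cost is one SAP sentence, one clarification and a small programming change to identify confirmatory and Rescue Visit samples. No new data are needed and HbA1c power is unchanged. Protocol 8.1 requires final SAP amendments before unblinding, so the sentence belongs there.
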